14.4 Health Authority Reporting (SUSAR reporting)

14.4.1 Definition of SUSAR

CONPET vs 14, 24th October 2018

SUSAR is defined as a suspected unexpected severe adverse event that is not listed in the IB for carfilzomib, and in the SPC for lenalidomide and dexamethasone.

14.4.2 Reporting of SUSAR

The sponsor-investigator is responsible for informing the regulatory authorities, the European Medicines Agency and the ethics committees of any individual case report of SAEs that are determined to be a SUSAR. The Investigator will ensure all relevant information is provided to the sponsor-investigator to allow the sponsor-investigator to meet their obligations to report the SUSAR.

Any life-threatening SUSAR will be reported by the sponsor as soon as possible (and not later than 7 days after the sponsor-investigator has become aware of the occurrence and with an up-date with relevant information within an additional 8 days). Any other SUSAR will be reported as soon as possible or within 15 days after the sponsor-investigator has become aware of it. The SUSARs will be reported to companies with SAE report form and to the Medical Agencies in the different countries.

A clear description of the suspected reaction should be provided along with an assessment as to whether the event is drug or disease related. The Sponsor-investigator shall notify the health authority by e-mail on a CIOMS form, of any unexpected fatal or life-threatening experience associated with the use of the drugs as soon as possible but no later than 7 calendar days after initial receipt of the information. SAE's will be reported 60 days after last study drug dose but SUSAR's will be reported 1 year after last study drug dose.

14.5 Non-Serious Adverse Events

A non-serious adverse event is an AE not classified as serious. Non-Serious adverse events \geq grade 2 will be collected and reported via annual safety reports and final study reports. These AEs will be collected until 30 days after the last dose of study treatment. The following non-serious adverse events will not be reported:

- A pre-existing condition that does not increase in severity; the pre-existing condition should be reported on the baseline concomitant diseases CRF
- AE's of CTCAE grade 1

- Abnormal laboratory values that have been recorded as being not clinically significant by the investigator in the source documents
- Nausea/vomiting
- Progression of the disease under study; complaints and complications as a result of disease progression

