Hematological toxicity: Neutropenia and thrombocytopenia: Lenalidomide is associated with anemia, neutropenia, febrile neutropenia, thrombocytopenia and pancytopenia. Grade 3 or 4 neutropenia and thrombocytopenia are the most common dose-limiting AEs. A complete blood cell count, including WBC count with differential, platelet count, hemoglobin and haematocrit, should be performed to monitor for cytopenias in accordance with the protocol during the study and cytopenias should be handled by protocol guidelines. Patients with neutropenia should be monitored for signs of infection. Patients and physicians are advised to be observant for signs and symptoms of bleeding, including petechiae and epistaxis, especially in case of concomitant medication susceptible to induce bleeding, a dose reduction of lenalidomide may be required.

Gastrointestinal disorders: Constipation, diarrhea, nausea, and vomiting were the most commonly reported gastrointestinal AEs during treatment with lenalidomide.

Hepatic disorders: Cases of transient liver laboratory abnormalities, predominantly transaminases, were reported in patients treated with lenalidomide. Treatment with lenalidomide should be interrupted and restarted once the levels return to baseline. Successful rechallenge without recurrence of liver laboratory elevations was reported in some patients. In post-marketing surveillance, a few cases of acute hepatic failure, including fatalities, were reported. The mechanism of reported hepatic toxicity remain unknown although, in some cases, pre-existing viral liver disease, elevated baseline liver enzymes, and possibly treatment with antibiotics might be risk factors.

Infections and infestations: Treatment-emergent AEs of infections, specifically pneumonia, are commonly seen with lenalidomide.

Cardiac disorders: Adverse events such as atrial fibrillation, myocardial infarction and heart failure have been reported with the use of lenalidomide from clinical studies and post-marketing surveillance. Patients with prior history and known risk factors for these AEs should be closely monitored.

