12.3.2 Dose modification guidelines for lenalidomide

The dose modification guidelines as summarized below are recommended to manage both hematological and non-hematological toxicity. Local investigators can decide to not follow this dose modifications if they feel it is not in the best medical interest of the patient.

Hematological toxicity present at start of study should not lead to dose reduction.

| Platelet counts | |
|---|--|
| Thrombocytopenia | |
| When Platelets | Recommended Course |
| Fall to <30,000/mcL | Interrupt lenalidomide treatment, follow CBC weekly |
| Return to \geq 30,000/mcL | Resume lenalidomide at next lower dose. Do not dose below 2.5 mg daily |
| For each subsequent drop <30,000/mcL | Interrupt lenalidomide treatment |
| Return to \geq 30,000/mcL | Resume lenalidomide at next lower dose. Do not dose below 2.5 mg daily |
| Absolute Neutrophil counts (ANC) | |
| Neutropenia | |
| When Neutrophils | Recommended Course |
| Fall to <1000/mcL | Interrupt lenalidomide treatment, follow CBC weekly |
| Return to \geq 1,000/mcL and neutropenia is the only toxicity | Resume lenalidomide at 25 mg daily or initial starting dose |
| Return to \geq 1,000/mcL and if other toxicity | Resume lenalidomide at next lower dose. Do not dose below 2.5 mg daily |
| For each subsequent drop <1,000/mcL | Interrupt lenalidomide treatment |
| Return to \geq 1,000/mcL | Resume lenalidomide at next lower dose. Do not dose below 2.5 mg daily |

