14.5.1 Laboratory Test Abnormalities

The following laboratory abnormalities should be captured and reported as appropriate:

- Any laboratory test result that is clinically significant or meets the definition of an SAE
- Any laboratory test result abnormality that required the subject to have study drug discontinued or interrupted
- Any laboratory test result abnormality that required the subject to receive specific corrective therapy.

Laboratory test abnormalities are provided to AMGEN via annual safety reports (if applicable), and interim or final study reports.

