16.6 Safety analyses

Safety analyses will be performed in the safety population. Safety analyses will be descriptive and presented as summary tables.

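### Sections 14.5 and 14.5.1 do not say which governs a laboratory value labelled not clinically significant, so AE-reported cytopenia rates may be understated and may vary by site

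*Protocol*

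**What the plan says.** Section 14.5 collects non-serious adverse events of grade 2 or higher. It then gives a list under the words "The following non-serious adverse events will not be reported". One entry is "AE's of CTCAE grade 1". Another is "Abnormal laboratory values that have been recorded as being not clinically significant by the investigator in the source documents". The laboratory entry carries no grade limit and no reference to 14.5.1.

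Section 14.5.1 sets three criteria for laboratory abnormalities to be captured and, as appropriate, reported. The first is "Any laboratory test result that is clinically significant or meets the definition of an SAE". The second criterion turns on what was done with study drug: "Any laboratory test result abnormality that required the subject to have study drug discontinued or interrupted". The third covers abnormalities for which the patient needed specific corrective therapy.

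The dose guidance decides which counts lead to an interruption. For platelets below 30,000/mcL or neutrophils below 1,000/mcL, 12.3.2 says: "Interrupt lenalidomide treatment, follow CBC weekly". The same section lets local investigators set the guidance aside in the patient's interest, and 12.2.1 does so for carfilzomib.

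On analysis, 16.6 says: "Safety analyses will be descriptive and presented as summary tables". It does not say whether cytopenia rates come from adverse event forms or from blood counts.

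**The concern.** The two sections give a site different instructions for the same value when it has been labelled not clinically significant and yet led to an interruption or to treatment. Beyond that overlap, a cytopenia that meets none of the action-based criteria in 14.5.1 is recorded or not according to one investigator's label, whatever its grade, unless it is serious.

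This matters because cytopenia is the toxicity that the protocol expects most. Section 2.3 says of lenalidomide: "Grade 3 or 4 neutropenia and thrombocytopenia are the most common dose-limiting AEs". Section 2.1 reports that, for carfilzomib, cytopenias were the only side effects to reach grade 3 or 4 in more than one patient in ten. Safety is a secondary endpoint in the synopsis, and 16.1 names it as a purpose of the study. The trial has one arm and five centres, so no comparator is affected equally by labelling habits.

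**Working it through.** The protocol states no figure on this point, so there is none to reproduce. The check sets the passages side by side, in units of 10⁹/L (30,000/mcL = 30; 1,000/mcL = 1.0).

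| Count | Carfilzomib (12.2.2) | Lenalidomide (12.3.2) | Route into the adverse event record |
|---|---|---|---|
| Platelets from 10 to below 30, no bleeding | continued at same dose | interrupted | 14.5.1 requires it; 14.5 excludes it if labelled not significant |
| Neutrophils 0.5 to 0.75 | continued at same dose | interrupted | as above |
| Neutrophils above 0.75 and below 1.0 | no action listed | interrupted | as above |
| Platelets above 30 | no action listed | no action listed | label only, unless corrective therapy is given or the event is serious |
| Neutrophils 1.0 or more | no action listed | no action listed | label only, same exceptions |
| Haemoglobin, any value | no action listed | no action listed | label only, same exceptions |

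Three things follow.

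1. **Overlap.** In the first three rows carfilzomib may continue, which makes a label of not significant possible, while the lenalidomide interruption brings the value under 14.5.1. The text does not settle which section wins.
2. **No action trigger.** In the last three rows the first criterion of 14.5.1 repeats the clinical-significance test used in 14.5. The other two criteria act only if drug was stopped or corrective therapy given. Otherwise the label alone decides.
3. **Discretion.** If the investigator does not interrupt lenalidomide, a count in the first three rows loses its interruption trigger and joins the second group. The opening of the Safety chapter says that the dose guidelines must be followed, but 12.2.1 and 12.3.2 allow departures.

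**Direction.** The label can only remove events, so any bias in rates taken from adverse event forms is downward.

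**Size.** Let s be the share of events that are labelled not significant and go unrecorded. Then recorded rate = true rate × (1 − s). The protocol gives no value for s. As starting rates only, take the frequencies in 2.3 for lenalidomide with dexamethasone, which are not split by grade and do not include carfilzomib.

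- Neutropenia 39.4%: s = 10% gives 39.4 × 0.90 = 35.5%; s = 50% gives 39.4 × 0.50 = 19.7%.
- Thrombocytopenia 18.4%: s = 10% gives 18.4 × 0.90 = 16.6%; s = 50% gives 18.4 × 0.50 = 9.2%.
- s = 0 leaves both unchanged.

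**What the data already allow.** The study procedures table schedules haematology on Day 1 of four cycles, Day 15 of four cycles, and at Visits D1 and D2: 4 + 4 + 2 = 10 counts per patient who completes treatment, the first of them on Cycle 1 Day 1. A rate computed from these does not depend on the label.

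**The case against.** The best defence is that 14.5.1 is a subsection of 14.5 and completes it, so the specific rule would naturally override the general one. On that reading the sections collide only when an investigator stops drug or gives treatment for a value and also calls it not significant, which should be unusual. The corrective-therapy criterion also covers cytopenias treated with transfusion or growth factor, both permitted in 12.6.2. Much of this stands. If 12.3.2 is followed and 14.5.1 prevails, neutrophils below 1.0 and platelets below 30 are captured. What remains is that no sentence says 14.5.1 prevails, and that it does not reach the cytopenias in the last three rows of the table.

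It can also be said that a clinical-significance filter is an ordinary choice and that tables of laboratory grades belong in the analysis plan, which is not shown. The second part is fair: that plan may already tabulate from counts. But 14.5 instructs sites and feeds the annual safety reports, and an analysis plan cannot tell sites which of two instructions to obey.

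A reader might infer more than the text supports:
- **That 14.5 discards every such value at any grade.** It does not. The list covers non-serious events only, and 14.5.1 requires values that led to interruption, discontinuation or corrective therapy.
- **That the cytopenia rates are understated.** This is not shown. Section 16.6 does not tie them to adverse event forms.
- **That the entry limits in 8.1 (neutrophils from 0.5, platelets 35) will make unreported low counts frequent.** Those limits do not say how many patients enter near them. Under 14.2 an adverse event must be new or a worsening, and 14.5 separately excludes pre-existing conditions that do not worsen. Leaving out unchanged entry counts is therefore correct.

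**Conclusion.** The point holds in a limited form. Two reporting rules overlap without an order of precedence, and some non-serious cytopenias enter the adverse event record only through a local label with no grade ceiling. Rates taken from adverse event forms may be too low and may vary by site. The size cannot be derived from the protocol: the figures above rest on an assumed share of 10% to 50% and on borrowed starting rates. The labelling bias is zero if no event is labelled away or if rates are tabulated from the scheduled counts. The primary endpoint and the reporting of serious events are not affected. The change is worth making because safety is a stated endpoint and the repair is small.

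**What to change.** - **Section 14.5:** add that the laboratory exclusion is subject to 14.5.1, and that it does not apply to new or worsened neutrophil, platelet or haemoglobin values of CTCAE grade 3 or higher.
- **Section 16.6:** add that haematological toxicity is tabulated as worst CTCAE grade per patient, with shift from Cycle 1 Day 1, using the counts already scheduled on Day 1 and Day 15 of each cycle and at Visits D1 and D2, whatever the clinical-significance label.

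The cost is slightly more adverse event recording at sites and one extra table from data already collected. Reported cytopenia rates may come out higher. Scheduled counts can miss a low point between visits, so the table supplements the adverse event listing and does not replace it. No dose rule changes.

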14.5.1 Laboratory Test Abnormalities

The following laboratory abnormalities should be captured and reported as appropriate:

- Any laboratory test result that is clinically significant or meets the definition of an SAE
- Any laboratory test result abnormality that required the subject to have study drug discontinued or interrupted
- Any laboratory test result abnormality that required the subject to receive specific corrective therapy.

Laboratory test abnormalities are provided to AMGEN via annual safety reports (if applicable), and interim or final study reports.

14.6 Pregnancy

If, following initiation of the investigational product, it is subsequently discovered that a study subject is pregnant or may have been pregnant at the time of investigational product exposure, including during at least 6 half-lives after product administration, the investigational product will be permanently discontinued in an appropriate manner (e.g., dose tapering if necessary for subject safety).

The investigator must immediately notify AMGEN and the sponsor-investigator of this event via the Pregnancy Surveillance Form within 24 hours and in accordance with SAE reporting procedures. Follow-up information regarding the course of the

pregnancy, including perinatal and neonatal outcome and, where applicable, offspring information must be reported on a Pregnancy Surveillance Form.

Any pregnancy that occurs in a female partner of a male study participant should be reported to AMGEN. Information on this pregnancy may also be collected on the Pregnancy Surveillance Form. Protocol-required procedures for study discontinuation and follow-up must be performed on the subject unless contraindicated by pregnancy (e.g., x-ray studies). Other appropriate pregnancy follow-up procedures should be considered if indicated.

14.7 Overdose

Definition of overdose in this study is any accidental dose higher than specified in the protocol. An overdose is defined as the accidental or intentional administration of any dose of a product that is considered both excessive and medically important. All occurrences of overdose must be reported as SAEs.

14.9 Other Safety Considerations

Any significant worsening noted during interim or final physical examinations, electrocardiograms, X-rays, and any other potential safety assessments, whether or not these procedures are required by the protocol, should also be recorded as a non-serious or serious adverse event, as appropriate, and reported accordingly.

14. DATA MONITORING

The monitoring of the study will be organized and led by [name] after agreement with the Steering Group of the study. In Sweden and Norway, independent monitors from Clinical Studies Sweden – Forum South at Skåne University Hospital will perform the monitoring. A monitoring plan describing the monitoring activities will be developed. In Denmark, monitors from the two GCP units (in Copenhagen and Odense) will carry out the monitoring.

Monitoring will be performed before, during and after the study, according to ICH-GCP guidelines, with emphasis on legal and safety data, plus endpoint and response evaluation.

Each main study center will be visited before starting the first patient; this prestudy visit will include information on the study, identification of the local study team, and

control of their knowledge of the GCP rules and the protocol regulations. Necessary documents in the investigator study file will be identified and controlled. The local handling of the study drug will also be controlled, with the study staff and the hospital pharmacy.

During the study, each center will be visited after inclusion of the first 1-2 patients and thereafter once or twice yearly. The local investigator will give the monitor direct access to the patients' hospital files, original laboratory data and Case Report Forms. At these visits, the monitor will control that the included patients' consent forms are obtained in correct time, and documented in the hospital files; that patients are included in accordance with the protocol; that adverse events are correctly documented and reported; that the data necessary for evaluation of response and relapse are collected and documented; and that the study drug handling is performed correctly.

After study termination, a final visit to each center will be performed to control that all data are correctly collected, that the CRFs are complete and reported to the study secretariat. The monitor will assist the local study investigator in preserving the study material according to GCP rules.

15.1 Handling of documents and data

All sites will enter data in a web-based electronic CRF, and the local investigator or study nurse can sign the CRF. There will be back-up of data at the data centre in Oslo, and all people working on the files will need login details from the sponsor-investigator. Documents that are essential for evaluation of study conduct and data quality will be filed in such a manner that they are protected from accidental loss. The sponsor-investigator will file all national essential regulatory documents relevant to the overall conduct of the trial. Local investigators will file all essential documents relevant to the conduct of the trial on site. Essential documents will be retained for 15 years after the end of the trial and the final presentation of the study. Source documents and medical records of patients should be retained for 15 years after the end of the trial. After this time, these documents will be handled by the site's guidelines regarding medical records.

15.2 Amendments

Any amendments to this protocol that seems appropriate, as the study proceeds (regarding safety, efficacy, conduction or scientific value of the study) will be agreed upon the coordinating and/or principal investigator and sponsor-investigator. Substantial amendments will be submitted to the Ethics Committee and the regulatory authority for written approval before the implementation of the amended version. Companies will be informed about possible amendments before sending to Ethics Committee and the regulatory authorities.

The sponsor-investigator will make an annual safety report that will be sent to the ethical committees and regulatory authorities, where the safety of the study will be judged and evaluated. A list of SAEs and SUSARs will be included.

15.3 Quality-of-Life

The Quality of life data will be handled by Quality of Life Research Centre, Odense (QoLRC-OUH) and will be stored in the Electronic data capture platform, REDCap database. The quality of life data collection of the protocol will be approved by Odense Patient Explorative Data Network (OPEN), University of Southern Denmark, Denmark, who has a license to the REDCap database. A Data Processing agreement will be obtained between the approval Data Protective Agency in Norway and OPEN and an OPEN license agreement will be obtained between OPEN and QoLRC-OUH as a representative for the sponsor and the sponsor.

15. STATISTICAL CONSIDERATIONS

16.1 Sample size determination

The objective of the study is to describe the proportion of patients still PET-positive after standard first line treatment in the Nordics, and to describe how many of these can become PET-negative after consolidation with KRd. The study is a phase 2 study looking at the feasibility and safety of this approach. Fifty PET-positive patients is considered acceptable to achieve this objective, see Table below for precision of the estimates with different proportions. We anticipate a 50% PET- CT-positivity after first line treatment in the total population, which amounts to 100 pts screened with PET-CT initially. 50 PET-CT+ patients will be included.

| Proportion | Confidence Interval |
|------------|---------------------|
| 0.1 | (0.043 - 0.214) |
| 0.2 | (0.112 - 0.330) |
| 0.3 | (0.191 - 0.438) |
| 0.4 | (0.276 - 0.538) |
| 0.5 | (0.366 - 0.634) |
| 0.6 | (0.462 - 0.724) |
| 0.7 | (0.562 - 0.809) |
| 0.8 | (0.670 - 0.888) |
| 0.9 | (0.786 - 0.957) |

16.2 Endpoint definitions

Primary endpoint:

- Change from PET-CT positivity to PET-CT negativity at visit D Proportion of PET-CT positivity after standard first line therapy

Secondary endpoints are

- Change from MRD positivity to MRD negativity at visit D, as assessed by 8-colour Euroflow multiparameter flow cytometry
- Overall response after each treatment cycle.
- Progression-free survival (PFS) as defined as time from treatment initiation to progression defined using IMWG criteria for progressive disease.
- Time to next treatment (TTNT) as defined as time from treatment initiation (start of cycle 1) to start of cycle 1 in next cancer treatment cycle.
- Overall survival (OS) as defined as time from treatment initiation (start of cycle 1) to time of death
- Quality-of-Life (section 15.3 and study flow chart)

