| 
Study Endpoints
 
Primary:
 
 - Proportion of PET-CT positivity after standard first line therapy - Change from PET-CT positivity to PET-CT negativity after 4 cycles of KRd consolidation. 
Secondary:
 
 - MRD negativity by 8-colour EuroFlow after 4 cycles of KRD consolidation. - Safety - Overall response rate - Progression-free survival (PFS) - Time to next treatment (TTNT) - Overall survival (OS) - Quality of life during and after KRD consolidation |
| 
Treatment schedule
 
Four cycles of Carfilzomib-Lenalidomide-Dexamethason
 
The carfilzomib dose is 20-20-36-36-36-36 mg/m² on day 1, 2, 8, 9, 15 and 16 in the first cycle. It will be increased to 36 mg/m² on days 1, 2, 8, 9, 15 and 16 in cycles 2-4.
 
The oral dexamethasone dose is 40 mg weekly throughout the study for patients under 75 years of age. 20 mg for patients over 75 years of age.
 
The Revlimid dose is 25 mg on days 1-21 in every cycle.
 |

Inclusion criteria (selected)

1. Prior confirmed diagnosis of multiple myeloma (2014).
2. Received standard first line treatment with at least partial response. Standard first line treatment is defined as VRD, VTD or VCD followed by ASCT, with or without lenalidomide maintenance
3. Carfilzomib naïve
4. Eastern Cooperative Oncology Group (ECOG) performance status 0-2.
5. Absolute neutrophil count (ANC) $\geq 0,5 \times 10^9/L$ and platelet count $>35 \times 10^9/L$.
6. At least very good partial remission (VGPR) from first line treatment

Exclusion criteria (selected)

1. Change of first line treatment because of stable or progressive disease.
2. Major surgery within 28 days before enrollment.
3. Radiotherapy within 14 days before enrollment.
4. Glucocorticoid therapy within the 14 days prior to inclusion that exceeds a cumulative dose of 160 mg dexamethasone or 1000 mg prednisone.
5. Patients who started treatment more than 12 month before screening
6. Central nervous system involvement.
7. Uncontrolled heart disease, including congestive heart failure (NYHA III-IV), uncontrolled angina pectoris, uncontrolled conduction abnormalities, acute diffuse infiltrative pulmonary disease, pericardial disease or myocardial infarction within 6 months prior to enrollment
8. Uncontrolled hypertension or uncontrolled diabetes despite medication
9. Active hepatitis B or C infection or known human immunodeficiency virus (HIV) positivity.

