12.2.1 Dose modification guidelines for carfilzomib

In a case of study-related adverse event, the clinical investigator must assess its possible relationship to carfilzomib, lenalidomide and dexamethasone.

Local investigators can decide to not follow this dose modifications if they feel it is not in the best medical interest of the patient.

| Carfilzomib dose reduction guidelines for toxicity and dose modification | | | |
|---|--------------------------------|--------------------------------|--------------------------------|
| | 1 st dose reduction | 2 nd dose reduction | 3 rd dose reduction |
| 36 mg/m ² | 27 mg/m ² | 20 mg/m ² | 15 mg/m ² |

If a patient requires an interruption of carfilzomib of more than four weeks this study patient will be removed from study; all exceptions to this must be discussed with principal investigator. If the carfilzomib dose is reduced once, it will be continued for at least one cycle. In case this cycle is tolerated, the dose level prior to reduction may be resumed by the investigator's discretion. If carfilzomib is stopped permanently due to toxicity, all study medication will be stopped and the patient will proceed to end-of-study visit.

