16.5 Statistical analyses

The primary parameter to be estimated is the proportion of patients with a negative PET-CT with 95% confidence limits by the Wilson method. The primary analysis will be performed on the mITT population.

Dichotomous endpoints will be handled as the primary parameter in addition to mixed model logistic regression for repeated measurements. Time to event endpoints will be presented using Kaplan-Meier plots, while repeated continuous endpoints will be analysed using linear mixed models. All parameters will be analysed both in the mITT and PP populations.

Unless otherwise specified, all estimates will be presented with 95% confidence limits. Parameter estimates might be compared to historical estimates, pre-specified prior to any analyses.

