16.7 Missing data

For dichotomous endpoints, missing data will be handled using worst case imputation. No imputation will be performed for time-to-event data, and incomplete registrations of event will be censored at last time of contact. Continuous endpoints will be analysed using mixed modes giving unbiased estimates under the assumption of missing at random.

Robustness analyses including complete case analyses, last observation carried forward, best case imputation and multiple imputation techniques might be considered if the rate of missing data is substantial.

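### Protocol 16.2 defines PFS by progression alone, so deaths without progression are censored and the reported quantity is time to progression

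*Protocol*

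**What the plan says.** PFS is listed among the secondary endpoints in the synopsis and defined in Protocol 16.2 as "Progression-free survival (PFS) as defined as time from treatment initiation to progression defined using IMWG criteria for progressive disease". In the same list, death appears only for survival: "Overall survival (OS) as defined as time from treatment initiation (start of cycle 1) to time of death".

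For analysis, 16.5 states: "Time to event endpoints will be presented using Kaplan-Meier plots". It names no competing-risk method. It also permits comparison of estimates with pre-specified historical values. For patients without a recorded event, 16.7 states: "No imputation will be performed for time-to-event data, and incomplete registrations of event will be censored at last time of contact".

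Elsewhere PFS is only named. The synopsis lists it, and sections 7 (study design) and 10 (end of study) mention follow-up for it. Section 16.4 mentions progression and death as examples of efficacy data that will mature later, not as a combined event.

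**The concern.** PFS is ordinarily a composite in which death from any cause counts as well as progression. The endpoint written here is the progression component alone, which is time to progression. The difference matters in a single-arm study, where the curve has no internal comparator and a reader will set it beside published PFS figures. An estimate that leaves out one type of failure will look better than one that counts it, even if the treatments perform equally.

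The protocol itself makes such deaths foreseeable. Section 9 lists death separately from progressive disease as a reason for withdrawal. Section 2.1.1 reports three fatal serious events in a once-weekly carfilzomib study, two of them not due to progression. That was a relapsed population on another regimen, so it shows that such deaths can happen and gives no rate for this trial.

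**Working it through.** **Step 1: reading the rules together.** Take a patient who dies with no IMWG progression.
- Under 16.2 the PFS event has not occurred, because progression is the only event.
- Under 16.7 there is no imputation, and follow-up without a registered event ends in censoring at last contact.
- Under 16.5 this observation enters a Kaplan-Meier plot as censored.

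No sentence says outright that deaths are censored for PFS. It follows from the three sections, and the protocol provides no other handling.

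**Step 2: direction.** With n patients at risk, a death counted as an event multiplies the curve by (1 − 1/n). If the death is censored, the factor is 1. From that death onward the written curve lies above the curve that counts it.

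**Step 3: the plan's own figure.** The protocol gives no median, event count or death rate for PFS. Its only design figure is the Wilson precision table for n = 50 in 16.1. The row for 0.7, with z = 1.96 and z² = 3.8416:
- centre = (0.7 + 3.8416/100) / (1 + 3.8416/50) = 0.738416 / 1.076832 = 0.686
- half-width = 1.96 × √(0.7 × 0.3/50 + 3.8416/10000) / 1.076832 = 0.123
- interval 0.562 to 0.809, as printed. The other eight rows also match.

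This table does not depend on the PFS definition. It serves below as a yardstick for sampling error.

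**Step 4: size at 24 months.** Assumptions, none from the protocol: constant hazards, 70% progression-free at 24 months by the written definition, and a non-progression death rate d of 1%, 2% or 4% per year.
- Progression hazard λ = −ln(0.70)/2 = 0.178 per year.
- PFS with death counted = exp(−2(λ + d)) = 0.70 × exp(−2d).
- Expected deaths without progression among 50 patients fully followed for 24 months = 50 × d/(λ + d) × (1 − PFS).

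| d per year | Written endpoint | PFS with death counted | Overstatement | Expected such deaths |
|---|---|---|---|---|
| 1% | 70.0% | 68.6% | 1.4 points | 0.8 |
| 2% | 70.0% | 67.3% | 2.7 points | 1.7 |
| 4% | 70.0% | 64.6% | 5.4 points | 3.2 |

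**Step 5: effect on the median.** If a share s of first events are deaths without progression, constant hazards give written median = true median / (1 − s). For an assumed true median of 36 months:

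| s | Written median | Written estimate at 36 months (true 50.0%) |
|---|---|---|
| 2% | 36.7 months | 50.7% |
| 5% | 37.9 months | 51.8% |
| 10% | 40.0 months | 53.6% |
| 20% | 45.0 months | 57.4% |

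The ratio of medians, 1.02 to 1.25, does not depend on the median assumed.

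**The case against.** **Censoring detail belongs in the SAP, which is not at hand.** Section 16.7 concerns incomplete event registrations and does not mention deaths under PFS. This is fair as far as fine censoring rules go. It does not cover the event itself, which 16.2 states explicitly and without death. A SAP that counted death would contradict the protocol.

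**The effect is small and the endpoint secondary.** This stands. The illustrated overstatement of 1.4 to 5.4 points compares with about 12 points either side in the protocol's own interval at 0.7. OS counts every death and will be reported beside PFS, safety is tabulated, and the historical comparison is optional with no PFS comparator named. These points limit the severity. They do not make the label correct, and the error runs in one direction only.

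**Stronger readings that the protocol does not support.**
- A reader might infer that patients stopped for toxicity are afterwards contacted only for survival, and so gain unassessed progression-free time. Section 12.2.1 says: "If carfilzomib is stopped permanently due to toxicity, all study medication will be stopped and the patient will proceed to end-of-study visit". It does not say that disease assessment ends there. Survival-only contact is tied to progression in section 10 and in the study procedures table, and 13.5 requires immunochemistry every two months until progression. At most 12.2.1 is ambiguous. For patients on the schedule, last contact should lie close to last assessment.
- A reader might infer that toxic deaths would raise the curve. Censoring leaves the estimate unchanged at that time and makes later drops larger through a smaller risk set. In Step 4 the written endpoint reads 70% at every death rate. The deaths are left out, not rewarded.
- A reader might infer that planned lenalidomide maintenance ends TTNT, which runs "to start of cycle 1 in next cancer treatment cycle". Maintenance is part of the planned sequence (section 7) and is continuous (12.4), so it has no first cycle. The natural reading excludes it, and saying so would only add clarity.

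**Conclusion.** The point holds. As written, the endpoint is time to progression under the name PFS, and it overstates PFS if any patient dies without progression. The direction rests on the text of 16.2, 16.5 and 16.7 alone. The size rests on assumed death rates and constant hazards: 1.4 to 5.4 points at 24 months for 1% to 4% per year, or a median too long by a factor of 1.02 to 1.25 when 2% to 20% of first events are such deaths. In transplant-eligible patients with at least a VGPR, the lower part of these ranges may be the more likely. The primary endpoint, the sample size and the precision table do not change. This is a should-fix on a secondary endpoint.

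**What to change.** In 16.2, define PFS as the time from start of cycle 1 to IMWG progression or death from any cause, whichever comes first. Naming start of cycle 1 also aligns the clock with OS and TTNT.

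In 16.7, censor PFS for patients alive and progression-free at the last adequate disease assessment, and keep last contact for OS.

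If the present quantity is the one wanted, call it time to progression.

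The cost is mainly wording. The synopsis provides for follow-up until death, and disease evaluation is already scheduled every second month until progression, so no new data are needed. Section 17.4 lists a change of endpoints among the significant changes that need approval, so the sponsor should allow for an amendment. The downside is that reported PFS becomes slightly less favourable.
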